During the Open-Label Extension Period, after 12 weeks (Week 28), topical corticosteroids and calcineurin inhibitors can be used, and details regarding therapy (ie, name, dose, frequency of administration, strength, duration of use) should be recorded.

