9.2.5. Open-Label Extension (Week 16-Week 68)

For subjects that remain on study treatment at Week 12, eligibility into the Open-Label Extension Period will be determined at Week 16 (coincides with the Double-Blind Treatment Period Safety Follow-Up Visit [Section 9.2.4]).

For eligible subjects that continue into the Open-Label Extension Period, following the administration of etrasimod 2 mg, a cardiac monitoring investigation will be performed [REDACTED] as outlined in Section 10.5.7.4.

If by approximately Week 28, within the Open-Label Extension Period, the subject has achieved suboptimal benefit from etrasimod treatment, both subjects and investigators should discuss the subject's continued participation in the study.

The recommended sequence of events presented for Double-Blind Treatment Period Day 1 (Section 9.2.2) should be followed for visits during the Open-Label Extension Period, where applicable, with study treatment being administered after blood sample collection.

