9.3. Early Study Treatment Termination

Subjects who stop taking their study treatment before the end of the Double-Blind Treatment or Open-Label Extension Periods will return to the study site for an EoT Visit within 1 week of the last study treatment administration. Subjects who stop taking their study treatment before the end of the Double-Blind Treatment Period are not eligible to participate in the Open-Label Extension Period. Visit assessments are detailed in the [REDACTED]. Study site staff will work with subjects who withdraw early to obtain as much follow-up data as possible. Lymphocyte counts should be monitored until returned to approximately baseline or stable. In the Double-Blind Treatment Period, whenever possible, subjects should continue in the study even if study treatment has been discontinued. Subjects who discontinue study treatment, but who consent to remain in the study will continue to comply with study visits and assessments.

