This plan will cover the analyses for: 1) the primary database lock after the completion of the Double-Blind (DB) Treatment Period; 2) the final database lock after the completion of the Open-Label Extension (OLE) Period. The plan will be finalized before the time of primary database lock and treatment unblinding. After that, the SAP may be amended to accommodate ad hoc analyses before the final database lock. Ad hoc analyses will be labeled as such on the output and identified in the Clinical Study Report.

2. Protocol Objectives

A. Primary Objective

To assess the efficacy of etrasimod monotherapy (1 or 2 mg) in subjects with moderate to severe atopic dermatitis (AD) during the DB Treatment Period.

B. Safety Objective

To assess the safety and tolerability of etrasimod monotherapy (1 or 2 mg) in subjects with moderate to severe AD during the DB Treatment Period.

C. Open Label Extension Objective

To assess the long-term safety, tolerability, and efficacy of etrasimod monotherapy (2 mg) in subjects with moderate to severe AD.

3. Study Endpoints

A. Primary Efficacy Endpoint

Percent change in Eczema Area and Severity Index (EASI) from Baseline to Week 12.

[REDACTED]

B. Key Secondary Efficacy Endpoints

- Proportion of subjects achieving EASI-75, defined as a 75% reduction of EASI from Baseline to Week 12.
- Proportion of subjects achieving a validated Investigator’s Global Assessment (vIGA) of 0 or 1 (on a 5-point scale) and a reduction from Baseline of ≥ 2 points at Week 12.

C. Secondary Efficacy Endpoints

- Percent change in weekly peak pruritus numeric rating scale (NRS) from an itch daily diary from Baseline to Week 12.
- Proportion of subjects with improvement (reduction) in weekly peak pruritus NRS ≥ 3 from an itch daily diary from Baseline to Week 12.
- Proportion of subjects achieving EASI-50, defined as a $\geq 50\%$ reduction of EASI from Baseline to Week 12.
- Proportion of subjects achieving EASI-90, defined as a $\geq 90\%$ reduction of EASI from Baseline to Week 12.
- Change and percentage change in percent body surface area (BSA) AD involvement total and for each body region from Baseline to Week 12.

D. Exploratory Efficacy Endpoints

- Change in Dermatology Life Quality Index (DLQI) from Baseline to Week 12.
- Change in Patient Oriented Eczema Measure (POEM) from Baseline to Week 12.
- Percent change in SCORing Atopic Dermatitis (SCORAD), total and by symptom (severity, and subjective symptoms), from Baseline to Week 12.

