Modified Full Analysis Set (mFAS)	The mFAS consists of all randomized subjects who received at least 1 dose of study treatment, have a baseline measurement, and have at least 1 post-randomization measurement. The mFAS is endpoint specific, therefore subjects included in the analysis set for 1 endpoint may differ from another endpoint, based on the baseline and post-baseline data.
Per Protocol Set (PPS)	The PPS consists of all subjects in the FAS who adhere to the protocol. The PPS will be used in sensitivity analyses of the primary and key secondary endpoints to evaluate the influence of major protocol violators and protocol deviators on the primary results. Specific reasons for warranting exclusion from this analysis set will be documented prior to database lock and may include, but are not limited to: 
 • Not meeting critical inclusion/exclusion criteria • Study treatment noncompliance • Receiving incorrect study treatment • Missing more than a defined number of visits while still on study • Chronic prohibited medication use while on study treatment
Treatment Completer Set (TCS)	The TCS includes subjects in EASI or vIGA specific mFAS who have completed 12 weeks of study treatment in DB Treatment Period.
Safety Set (SAF)	The SAF includes all randomized subjects who received at least 1 dose of study treatment.
[REDACTED]	[REDACTED]
Post Hoc Analyses Set (PHAS)	The PHAS excludes 9 subjects from the Full Analyses Set in the 2 mg treatment group with unwarranted dose interruption due to lymphocyte decrease between week 4 and 12
OLE Period	
OLE Safety Set (OLE SAF)	The OLE SAF includes all subjects who enrolled in the OLE Period and received at least one dose of etrasimod. All safety

	
and efficacy analysis in the OLE Period will be performed over OLE SAF. For the analyses of efficacy endpoints, subjects will further be required to have at least one efficacy measurement in the OLE Period. Therefore, efficacy evaluable set is endpoint specific.

H. Missing Data

In order to analyze primary and secondary efficacy endpoints at Week 12 in the FAS, the handling of missing data and rescue medication uses are specified in Section 8.B - 8.C. No imputation will be implemented for exploratory efficacy and safety endpoints. The handling of missing reporting information for safety assessments are specified in Section 9.

I. Data Display Characteristics

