The scores from the 7 questions are added up to give an overall POEM score (0-28). An overall POEM score of 0-2 = ‘clear/almost clear’, 3-7 = ‘mild’, 8-16 = ‘moderate’, 17-24 = ‘severe’, and 25-28 = ‘very severe atopic eczema’.

- **DLQI** is a 10-item patient-reported outcome (PRO) measure that assesses the extent to which the skin condition has affected the subject’s quality of life over the past week, including 6 domains (daily activities, personal relationships, symptoms and feelings, leisure, work/school, and treatment). Total score (0-30) will be calculated as the sum of 10 questions with each ranging from 0 to 3. The scoring of each answer is as follows:

Very much	Scored 3
A lot	Scored 2
A little	Scored 1
Not at all	Scored 0
Not relevant	Scored 0
Question unanswered	Scored 0

Question 7	Question 7A	Score
Yes	Any response	3
No	A lot	2
No	A little	1
No	Not at all	0
Not relevant	Any response	0

[figure not shown]
If one question is left unanswered this is scored 0 and the scores are summed and expressed as usual out of a maximum of 30. If two or more questions are left unanswered the total DLQI score is missing. If question 7 is answered ‘yes’ or ‘not relevant’, then the answer of 7a will be ignored.

B. Primary Efficacy Outcome Analysis

The primary endpoint of percentage change in EASI from Baseline to Week 12 will be analyzed based on the FAS using an analysis of covariance (ANCOVA) model. The ANCOVA model will include treatment group as factors, Baseline EASI score and the two randomization factors of baseline vIGA (3 versus 4) and

region [REDACTED] as covariates. EASI scores after rescue medication use will be set to missing. All missing EASI scores at scheduled visits up to Week 12 will be imputed using a multiple imputation (MI) technique with a fully conditional specification (FCS) method and predictive mean matching (PMM) for EASI scores (Heitjan 1991, van Buuren 2007). The rescue medications considered for the purposes of efficacy analysis will include topical and systemic corticosteroids used during the DB Treatment Period of the study.

For MI, 100 imputation models will be generated, including treatment, baseline vIGA (3 versus 4), region [REDACTED] baseline EASI score, and EASI scores at the previous scheduled visits. Percent change in EASI at Week 12 will be derived from the imputed EASI values.

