 CMH=Cochran-Mantel-Haenszel; NRS= Numerical Rating Scale; BSA=Body Surface Area; ANCOVA=Analysis of Covariance; MMRM=Mixed Model with Repeated Measures.

F. OLE Period Efficacy Analysis

The following endpoints will be assessed in the OLE Period:

- Continuous variables: observed value and change (percent) from Baseline in EASI, SCORAD, BSA, pruritus NRS, POEM, DLQI, and PGA
- Dichotomous variables: EASI-75, vIGA

The above variables will be summarized by visit using descriptive statistics based on the applicable analysis set, with following considerations:

- Only observed cases will be used with no imputation of missing data
- Summaries will be provided for 1 treatment group (“Total”) in OLE Period and also by original treatment groups (“Etrasimod 1mg”, “Etrasimod 2mg” and “Placebo”) in DB Treatment Period
- Change from baseline in continuous variables will be analyzed on change from DB baseline and change from OLE baseline, respectively

For OLE Period, subgroup analyses of main efficacy outcomes (EASI, vIGA, NRS, BSA) will be performed in the following categories:

- Week 12 EASI-75 responders versus non-responders
- Week 12 vIGA responders versus non-responders
- EASI score at DB baseline (\leq or $>$ median)
- Percent BSA AD involvement at DB baseline (\leq or $>$ median)

G. Efficacy Analysis on Subgroups of Subjects

Subgroup analyses of primary and key secondary endpoints for the DB Treatment Period will be conducted for each of the following groups:

- Sex (male, female)
- Race (White, Other)
- Age (\leq or $>$ median)
- Baseline vIGA (3 or 4)
- Baseline EASI score (\leq or $>$ median)
- Baseline percent BSA AD involvement (\leq or $>$ median)

9. Safety Analyses

Safety analyses will use data from the SAF for DB Treatment Period and OLE Safety Set for OLE Period. For the DB Treatment Period, summary will be done on the 3 treatment groups; for the OLE Period, summary will be done on 1 treatment group in the OLE Period and 3 subgroups in the DB Treatment Period. Week 16 is the last

scheduled visit in DB Treatment Period and first scheduled visit in OLE Period. Overall (DB + OLE) summaries will be provided as detailed below.

A. Exposure and Compliance

The following exposure and compliance parameters will be defined and summarized for DB treatment and OLE Periods separately, and for overall using descriptive statistics:

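### Open-label response at Weeks 32 to 68 is summarised on observed cases only and may overstate monotherapy response by an unknown amount

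*SAP*

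**What the plan says.** - **Objective (SAP 2.C):** "To assess the long-term safety, tolerability, and efficacy of etrasimod monotherapy (2 mg) in subjects with moderate to severe AD".
- **Analysis (SAP 8.F):** by-visit descriptive summaries, with the rule "Only observed cases will be used with no imputation of missing data". Table 3 gives the OLE Safety Set with observed cases, and its sensitivity column reads N/A. Protocol 11.9 adds no correction.
- **Denominator (SAP 5.G, Table 2):** for efficacy, "subjects will further be required to have at least one efficacy measurement in the OLE Period", so the set differs by endpoint.
- **Week 28 prompt (Protocol 9.2.5):** if by about Week 28 "the subject has achieved suboptimal benefit from etrasimod treatment, both subjects and investigators should discuss" whether the subject carries on in the study.
- **Topical therapy (Protocol 6.8.2):** in the OLE, "after 12 weeks (Week 28), topical corticosteroids and calcineurin inhibitors can be used".
- **Rescue rule (SAP 8.B):** the medications that count as rescue for efficacy analysis are "topical and systemic corticosteroids used during the DB Treatment Period of the study". Nothing equivalent is written for the OLE, and calcineurin inhibitors are not on the list.
- **Follow-up after stopping treatment (Protocol 9.3):** "In the Double-Blind Treatment Period, whenever possible, subjects should continue in the study even if study treatment has been discontinued". For the OLE, Protocol 9.2.6 gives an early stopper an end-of-treatment visit and a safety follow-up visit, and the latter is also the end of study for that subject.

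**The concern.** Two things can change at about the same week, and both can push the reported response rate upward. If subjects who are doing poorly leave more often than those doing well, the denominator loses non-responders. If some who stay improve because of a topical steroid or calcineurin inhibitor, their scores enter the numerator as ordinary observed response, although the objective is about monotherapy. The visits affected are Weeks 32, 40, 48, 56 and 68.

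The late EASI-75 and vIGA percentages are the OLE's efficacy result for response. They are also not on the same footing as the Week 12 rates, because SAP 8.C counts missing and post-rescue data for these same two endpoints as non-response. A reader who sets Week 12 beside Week 68 would be comparing two different quantities.

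**Working it through.** **Inputs.** The documents give no OLE response, exit or topical-use rate, so there is no planned OLE figure to reproduce. The dropout allowance of up to 25% in SAP 4.C belongs to the double-blind sample size. All rates below are therefore assumptions.

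Let *p* be the share who would respond at a late visit if all stayed on monotherapy, *xn* the share of non-responders who have left, and *xr* the share of responders who have left.

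**Without topical use**

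- Observed-case rate: OC = p(1−xr) / [p(1−xr) + (1−p)(1−xn)]
- Fixed-denominator rate, leavers counted as non-responders: FD = p(1−xr)
- Excess of OC over the truth: OC − p = p(1−p)(xn−xr) / [p(1−xr) + (1−p)(1−xn)]

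Three facts follow.

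1. FD equals OC times the share of subjects with data, so OC can never be below FD.
2. OC exceeds the true rate only if xn > xr. The excess is zero when xn = xr, and the sign reverses if responders leave more often.
3. FD falls below the true rate by p × xr, because responders who leave are counted as failures.

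| p | xn | xr | OC | FD | OC − p (points) | FD − p (points) |
|---|---|---|---|---|---|---|
| 40% | 10% | 10% | 0.36/0.90 = 40.0% | 36% | 0 | −4 |
| 40% | 20% | 10% | 0.36/0.84 = 42.9% | 36% | +2.9 | −4 |
| 40% | 40% | 10% | 0.36/0.72 = 50.0% | 36% | +10.0 | −4 |
| 40% | 50% | 10% | 0.36/0.66 = 54.5% | 36% | +14.5 | −4 |
| 30% | 40% | 10% | 0.27/0.69 = 39.1% | 27% | +9.1 | −3 |

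**With topical use.** Take p = 40%, xn = 40%, xr = 10%. Suppose 30% of the remaining non-responders use topicals and 30% of those users become observed responders. The remaining non-responders are 0.60 × 0.60 = 0.36, and the added responders are 0.36 × 0.30 × 0.30 = 0.0324.

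- OC = (0.36 + 0.0324)/0.72 = 54.5%
- FD with only leavers as failures = 0.3924 = 39.2%
- FD with topical use also counted as failure = 36.0% (assuming that no responder used topicals)

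**Range.** The assumptions were varied as follows: p from 30% to 50%, xn from 20% to 60%, xr = 10%, and topical use and conversion of none, 30%/30% or 50%/50%. The excess of OC over p ran from about 2.5 points (p = 30%, xn = 20%, no topicals: 0.27/0.83 = 32.5%) to about 32 points (p = 30%, xn = 60%, 50%/50%: 0.34/0.55 = 61.8%). In every case of this grid non-responders leave at least twice as often as responders, so it shows the size of the effect only if exit is differential.

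**The case against.** The strongest reply is that the bias is conditional. Week 28 calls for a discussion and sets no withdrawal rule, and topicals are permitted, not required. A reader might infer from the two provisions that late response is inflated as a matter of fact, or that poor responders are removed by design. The documents do not support either reading. This part of the objection stands.

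A reader might also take the gap between 54.5% and 36%, which is 18.5 points, as the inflation. It is not. Of that gap, 14.5 points lie above the assumed truth and 4 points are the fixed-denominator method's own downward bias.

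Some of the information is already planned. Protocol 11.9 calls for the number of observations by visit, SAP 7.A tabulates discontinuation by reason, and SAP 9.B summarises OLE concomitant medication and lists rescue therapy. SAP 8.F also splits OLE outcomes by Week 12 response. So it would be wrong to say that attrition is hidden. What is missing is a link between exit or topical use and response at each visit. The discontinuation reasons in Protocol 8.1 and 8.2 have no category for lack of efficacy, so the disposition table may not supply that link.

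A leaver may also contribute a last score at the end-of-treatment visit, because SAP 5.C assigns assessments to analysis visits. Whether EASI and vIGA are done at that visit cannot be seen in the public text. Even so, one score near exit does not fill the later visits.

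Finally, the extension is uncontrolled and descriptive, and response under permitted concomitant therapy is a legitimate thing to summarise. That is a reason to keep the observed-case table. It does not make that table an estimate of monotherapy response.

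**Conclusion.** The point holds as a modest one. Late OLE EASI-75 and vIGA rates on observed cases may overstate long-term monotherapy response, by an amount the documents do not allow one to state. The excess over the true rate is zero if exit is unrelated to response and no topicals are used. On the assumed exit rates tabulated it runs from 0 to 14.5 points without topical use, and effective topical use adds to it. What needs no assumption about who leaves is that the observed-case rate cannot be lower than a rate on the same subjects that counts missing as non-response, and is higher whenever there are observed responders and anyone is missing. No test depends on this, and the Week 12 primary and key secondary results are untouched.

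**What to change.** Keep the observed-case summaries in SAP 8.F and add a supplementary by-visit table of EASI-75 and vIGA response with all OLE Safety Set subjects as the fixed denominator, in two versions:

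1. Subjects who have left the OLE or have no data at the visit count as non-responders.
2. As in version 1, and visits after use of topical corticosteroids, calcineurin inhibitors or systemic AD therapy also count as non-response.

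Beside each visit, show the number of subjects on such therapy. State in the SAP that the table is a conservative bound and can understate response, for example where subjects leave for reasons unrelated to efficacy, such as the COVID-19 withdrawals foreseen in SAP 11.B. The table does not address the continuous OLE outcomes, which stay on observed cases.

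The cost is one extra table set from data already recorded, and a less favourable late response figure. No clinical rule changes. SAP section 1 allows amendment for ad hoc analyses before the final database lock, labelled as such.

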10.5.8. Adverse Events

10.5.8.1. Definitions

10.5.8.1.1. Adverse Event

An AE is any untoward medical occurrence that does not necessarily have a causal relationship with this treatment. An AE can therefore be any unfavorable and unintended sign, symptom, or disease temporally associated with the use of a medicinal product, whether or not considered related to the medicinal product.

AEs can include, but are not limited to, any of the following:

- Unfavorable changes in general condition
- Subjective or objective signs/symptoms
- Concomitant disease or accidents
- Clinically relevant adverse changes in laboratory parameters over the course of the study
- Pre-existing conditions that worsen in severity, increase in frequency, or have new signs/symptoms

Information on the grading and management of laboratory abnormalities according to assessment severity is provided in [Appendix 2](#) and [Appendix 3](#), respectively.

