10.5.8.1.5. Severity

The severity of each AE will be assessed at the onset by a nurse/or physician. When recording the outcome of the AE, the maximum severity of the AE experienced will also be recorded. The severity of each AE will be graded according to the Common Terminology Criteria for Adverse Events:

Grade 1	Mild; asymptomatic or mild symptoms; clinical or diagnostic observations only; intervention not indicated.
Grade 2	Moderate; minimal, local or noninvasive intervention indicated; limiting age-appropriate instrumental activities of daily living.
Grade 3	Severe or medically significant but not immediately life-threatening; hospitalization or prolongation of hospitalization indicated; disabling, limiting self-care activities of daily living (eg, preparing meals, shopping for groceries or clothes, using the telephone, managing money).
Grade 4	Life-threatening consequences, urgent intervention indicated.
Grade 5	Death related to an AE.

Additional information on CTCAE grading of AEs is provided in [Appendix 2](#).

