10.5.8.2.2. Recording Adverse Events

The AE reporting period for safety surveillance begins when the subject is initially included in the study (date of first signature of informed consent) and continues up to 30 days after the last study treatment administration. If an AE is not resolved or stabilized by this time, the Sponsor in consultation with the investigator will decide whether to continue to monitor the AE or closeout the event in the database if no further follow-up is necessary.

Any SAE suspected to be related to the study treatment must be reported whenever it occurs, irrespective of the time elapsed since the last administration.

Investigator and study personnel will record all AEs and SAEs whether received through an unsolicited report by a subject, elicited during subject questioning, discovered during physical

examination, laboratory testing, and/or other means by recording them on the eCRF and SAE Report Form, as appropriate. The following information should be recorded on the AE eCRF:

- Description including onset and resolution dates
- Whether it met SAE criteria
- Severity
- Relationship to study treatment or other causality
- Outcome

For SAEs, events occurring secondary to the primary event should be described on the eCRF in the narrative description field.

The following should be considered when recording SAEs:

- Death is an outcome of an event. The event that resulted in the death should be recorded and reported on the eCRF.
- For hospitalizations, surgical, or diagnostic procedures, the illness leading to the surgical or diagnostic procedure should be recorded as the SAE, not the procedure itself. The procedure should be captured in the narrative as part of the action taken in response to the illness.

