11.8.2. Adverse Events

All AEs will be coded using the Medical Dictionary for Regulatory Activities.

For each treatment group, the proportion of subjects with treatment-emergent AEs (TEAEs) will be summarized overall, by severity, and by relationship to study treatment. SAEs will also be summarized by treatment group. A TEAE is defined as:

- An AE that occurs after initiation of study treatment that was not present at the time of treatment start.
- An AE that increases in severity after the initiation of study treatment, if the event was present at the time of treatment start.

Any AE occurring before the first dose of study treatment will be summarized separately.

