- All medications that start in the OLE Period are considered as concomitant.

Prior medications/therapies for DB Treatment Period will be summarized by treatment using WHO Drug Dictionary (WHO-DD) Anatomical-Therapeutic-Chemical (ATC) classification and preferred term (PT). The highest available level of ATC among ATC 1-4 will be presented. For example, if ATC 1, ATC 2 and ATC 3 are available, the summary table and subject listing will present ATC 3. Concomitant medications/therapies will be summarized for DB Treatment Period, OLE Period and overall using ATC and PT.

C. Adverse Events

All AEs will be coded using MedDRA Version 23.0 March 2020. A treatment-emergent AE (TEAE) is defined as:

- Any reported AE that occurs after initiation of study treatment that was not present at the time of treatment start.
- All AEs that occur in the OLE Period are considered as TEAEs.

For the determination of TEAEs, the following rules regarding the partial start date will be applied and Baseline below refers to baseline in DB Treatment Period:

- If only the year was recorded, and it is before Baseline, it is a non-TEAE; if year is the same or after Baseline, it is assumed to be a TEAE.
- If the day is missing, but month and year are before Baseline, it is a non-TEAE; if the month and year are the same as Baseline, it is assumed to be a TEAE; if the month and year are after Baseline, it is a TEAE.
- If start date is after Baseline, it is a TEAE regardless.

If the relationship to treatment is missing, the event will be conservatively considered as being related to study drug. If the severity is missing, a separate

category of missing severity will be included in the summary table, and no imputation of severity will be performed.

AE profile will be provided (for DB Treatment Period, OLE Period, and overall), by treatment group and overall as follows:

- All AEs
- Non-TEAEs (for DB Treatment Period and overall)
- All TEAEs
- Serious AEs
- Non-Serious TEAEs
- TEAEs leading to study treatment discontinuation
- TEAEs leading to study treatment interruptions
- TEAEs related to study treatment. This will include TEAEs with a drug relationship of “Probably Related” and “Related”

Summaries of the incidence of TEAEs (for DB Treatment Period, OLE Period, and overall), will be displayed by treatment according to the following:

- TEAEs by SOC in alphabetical order and PT in descending order of frequency (in etrasimod 2mg, etrasimod 1mg, and then placebo)
- SAEs by SOC and PT

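### SAP 9.C drops the protocol's worsening limb from the TEAE definition without declaring it, so a screening-onset AE that worsens on treatment under one record becomes a non-TEAE

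*SAP*

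**What the plan says.** Protocol 11.8.2 defines a TEAE by two limbs. The first covers events that arise after treatment starts and were not there before. The second reads: "An AE that increases in severity after the initiation of study treatment, if the event was present at the time of treatment start". The same section adds that AEs before the first dose are summarised separately.

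SAP 9.C gives its own definition in two bullets. The first is "Any reported AE that occurs after initiation of study treatment that was not present at the time of treatment start". The second makes every AE in the open-label extension a TEAE and so does nothing for the double-blind period. Rules for partial start dates follow, ending with "If start date is after Baseline, it is a TEAE regardless". None of them refers to a change in severity.

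SAP Section 11 has two entries, on correlations among efficacy endpoints and on COVID-19. Neither concerns the TEAE definition.

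Three protocol provisions on AE recording also bear on this:

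- **10.5.8.2.2, window:** "The AE reporting period for safety surveillance begins when the subject is initially included in the study", which it specifies as the date consent is first signed.
- **10.5.8.1.5:** severity is assessed at onset, and "When recording the outcome of the AE, the maximum severity of the AE experienced will also be recorded".
- **10.5.8.1.1:** the examples of AEs include "Pre-existing conditions that worsen in severity, increase in frequency, or have new signs/symptoms".

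**The concern.** The SAP wording excludes exactly the events that the protocol's second limb was written to include. A programmer working from SAP 9.C would code the shorter rule, and nothing in the SAP would alert a reader of the tables that the definition differs from the protocol's.

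Safety and tolerability in the double-blind period is a stated objective, and the TEAE tables are its main AE summaries. The omission can only lower TEAE counts. The SAP leans the other way elsewhere in the same section: "If the relationship to treatment is missing, the event will be conservatively considered as being related to study drug", and a partial start date in the Baseline month is taken as treatment-emergent. Those rules deal with missing data rather than with the definition, so they do not prove the omission was an oversight, but the contrast is worth noting.

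**Working it through.** The plan gives no figure to reproduce. The check is to apply both definitions to the possible cases and then follow the discordant case through the outputs.

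**Step 1. Classification under each document (double-blind period)**

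| Case | Protocol 11.8.2 | SAP 9.C |
|---|---|---|
| Onset after first dose | TEAE (first limb) | TEAE |
| Onset between consent and first dose, no later worsening | Not a TEAE | Non-TEAE |
| Screening onset, open at first dose, worsens on treatment, worsening entered as a new AE with a post-dose start date | TEAE | TEAE (start date after Baseline) |
| Screening onset, open at first dose, worsens on treatment, kept on the same record | TEAE (second limb) | Non-TEAE |

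Only the last row differs. The exclusion comes from the SAP's definition bullet. The date rules merely settle partial start dates.

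**Step 2. Can that row occur?** Screening lasts up to 4 weeks and AEs are recorded from consent, so pre-dose AEs will be in the database. Because the maximum severity of an AE is to be recorded with its outcome, one record can carry a later worsening. The documents do not say whether a worsening must open a new record.

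**Step 3. Where the event goes**

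- *Absent from:* the TEAE tables by SOC/PT, by maximum CTCAE severity and by relationship, and the TEAE rows of the AE profile, including those for discontinuation and interruption. This applies to the double-blind and the overall summaries.
- *Still in:* the All AEs and Non-TEAEs rows, the AE listings, the listing of AEs leading to discontinuation and, if serious, the Serious AEs row and SAE listing.

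**Step 4. Size.** The planned arm is 40 subjects (Protocol 11.2). The number of affected subjects is assumed, because the documents give no basis for it.

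- Per arm, omitted subjects / 40: 0/40 = 0; 1/40 = 2.5; 2/40 = 5.0 percentage points.
- If only 38 of the 40 were dosed (an illustrative assumption): 1/38 = 2.6 points.
- Between arms, (omitted in arm A − omitted in arm B) / 40: zero if the numbers are equal, 2.5 points if they differ by one.

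The All TEAEs row loses a subject only if that subject has no other TEAE. A preferred-term, discontinuation or interruption row loses the subject unless another TEAE of theirs falls in the same row.

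**The case against.** Five points can be made for the plan.

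1. **The SAP says in its Introduction that it will not repeat every protocol definition.** This would help if 9.C were silent or deferred to the protocol. Instead 9.C states its own definition, and that definition conflicts, so the defence fails.

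2. **The event reaches more summaries than those listed above.** SAP 9.A counts subjects with dose interruptions due to AEs, SAP 7.A tabulates treatment discontinuation by reason, and SAP 9.C summarises Targeted Medical Events with no stated restriction to TEAEs. This stands and narrows the practical loss, since an event that stops or interrupts treatment is still visible. It does not put the event back into the TEAE tables or the TEAE-labelled rows.

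3. **Protocol 11.8.2 itself has pre-dose AEs summarised separately, and a single record with screening onset fits that sentence too.** It does not cancel the express worsening limb in the same section. It does mean that repaired wording should say which rule governs such a record.

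4. **Several conditions must hold together:** onset in screening, open at first dose, worse on treatment, and one record. If sites open a new record for each worsening, nothing is lost. This stands, and it is why the number affected is unknown and may be zero.

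5. **Treating maximum grade above onset grade as post-dose worsening goes further than the protocol, which requires the increase to follow the start of treatment.** This is fair. Such a rule is justified only as a fallback where the timing of the worsening was not captured, and it may over-count.

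**Conclusion.** The SAP is wrong as written on this point. It omits one of the protocol's two TEAE limbs for the double-blind period and does not declare the change. The conflict is certain from the text. Its numerical effect is not: it depends on how sites record a worsening and on how many AEs meet all the conditions, neither of which the documents settle.

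The effect is likely to be small, and the events stay visible elsewhere. At 2.5 points of an arm per subject, though, one or two cases would show in a TEAE table, and an imbalance between arms would carry into the comparison. It should be fixed because it concerns a core safety definition and the repair is cheap.

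**What to change.** 1. **Restore the limb in SAP 9.C.** Add, for example: *or an AE present at treatment start that increases in CTCAE grade after first dose*. State that the partial-date rules do not override it, and that an AE meeting it is counted as a TEAE rather than only in the separate summary of pre-dose AEs.

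2. **Check which grades the AE eCRF holds.** Protocol 10.5.8.1.5 implies both onset and maximum grade. The list in Protocol 10.5.8.2.2 introduced by "The following information should be recorded on the AE eCRF" has a single severity item.

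3. **Specify the derivation.** Identify post-dose worsening from a dated severity change or from a new record. Where only onset and maximum grade exist for an AE open at first dose, count it as a TEAE if the maximum exceeds the onset grade, unless the worsening is known to precede first dose. Report how many events enter by this fallback.

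4. **Rerun the double-blind and overall TEAE outputs.**

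5. **If the narrower definition was intended,** keep it, but declare and justify it in SAP Section 11.

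The cost is one sentence in the SAP, a check of the eCRF fields, one derivation and a rerun. If only one grade per AE was captured, the screening-onset AEs still open at Day 1 need manual review. The downside is that a few AEs that peaked before dosing may be counted as treatment-emergent, which errs in the conservative direction for safety.
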